
6) Study Endpoints

The primary study endpoint will be after completion of study (after surgery and survey completion) of 252 patients (126 in each treatment arm). Secondary endpoints include time to PACU clearance and time to hospital discharge. Because the intervention is a single-shot injection, there are no specific safety endpoints. Please see below for a discussion of potential adverse from the pectoralis nerve blocks.

7) Procedures Involved

Subjects presenting for immediate breast reconstruction and meeting inclusion criteria will be approached pre-operatively to make them aware of the study. On the day of surgery, patients will be asked to sign consent for the study. Patients who sign consent will then undergo randomization to a study arm (pre-op placement of intra-op catheter placement). Randomization will be done by study personnel using the i-phone application “Randomizer.” Randomization will follow a blocked scheme; that is, if one patient is randomized to the anesthesia block group, the next will automatically get the catheter treatment. This will ensure equal numbers in both study arms. After consent and randomization is complete, patients will be told of their study arm. Patients will then be asked to fill out a pre-operative pain survey discussing their baseline level of breast pain.

For those randomized to the pre-op placement arm, anesthesia will perform this block prior to surgery but after their pre-operative survey is complete. The anesthesia

PROTOCOL TITLE:

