With respect to the surveys, Redcap is a mature, secure web application that has been used successfully by many other investigators at our institution to collect secure survey data.

Data analysis will be done using <http://vassarstats.net>. Statistical comparisons will be performed across the study groups using T-test for two-group comparisons.

All research personnel will be up to date with their HIPAA training.

For our power analysis, we set our alpha = 0.05 and beta (power) = 0.8. Using the Bashandy et al. paper¹, the mean morphine requirement in the PACU was 2.9 ± 1.861 mg for the Pecs block group, and 6.9 ± 1.861 mg for the control group ($p < 0.001$). Based on our preliminary experience with pre-operatively placed pecs blocks, we estimate that they work well about 70% of the time. If we hope to see a 20% improvement with more accurate plane targeting, then our average morphine requirement in the intra-operative placement group would be 2.3 mg. Therefore, we would have to enroll 126 patients in each arm to have an 80% chance of seeing a difference, if there truly is one.

9) Provisions to Monitor the Data to Ensure the Safety of Subjects

The EMR of every subject who completes the injection portion of this study will be assessed within 24 hours of pectoralis nerve block placement. Any untoward events, such as intravascular injection, allergic reaction, pneumothorax or other unanticipated event will be assessed for its causative relationship to the pectoral nerve block . We anticipate these to all be very unlikely, as the current literature on the pectoralis nerve blocks report a 0% complication rate (see citations, above). If a serious adverse event occurs, these will be reported immediately to the IRB and will be a trigger for an immediate suspension in enrollment and a review of the injection protocol with the Chiefs of both the Departments of Anesthesiology and Surgery. If any performer error can be identified and corrected, then with approval from the departments enrollment will continue. If not, the study will be terminated.

We will cumulatively review the data after 20 subjects in each study arm have been enrolled, and then again at 50 patients, 75 patients, 100 patients, and 126 patients.

10) Withdrawal of Subjects

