There are limited circumstances in which a patient would be withdrawn from research, particularly without their consent. The only circumstance would be in the case of aborted tissue expander placement. If the plastic surgeon does not feel that the mastectomy flaps can support the added stress of an expander, then the plastic surgery portion of the procedure is aborted (standard protocol). In this circumstance, the pre-op block arm will already have gotten a block. No intra-operative catheters will be placed. After awakening from anesthesia, the patient will be alerted to their expulsion from the study, and no other data would be collected regarding their hospital stay, and no survey information collected.

Of note, a single patient was enrolled into the control arm of the study prior to this arm being abolished. This patient's survey data has already been collected but will not be used for data analysis. Their hospital data will not be collected.

11) Risks to Subjects

The main foreseeable risk to study subjects is that the nerve block would not work well. In this event, subjects would be appropriately treated with adjunctive pain medications.

Two very rare risks – never reported in the literature, so currently theoretical rather than described – are intravascular injection and pneumothorax, as outlined above. These could have potentially serious consequences, such as bupivacaine toxicity (at worst, leading to hypotension or seizure) or hypoxemia requiring chest tube placement and potentially other procedures. However, pectoralis nerve blocks have been in use for over 5 years, and more risky blocks, including the paravertebral block and intercostal block (both of which have higher rates

PROTOCOL TITLE:

reported of the above complications) for over 30 years. Therefore, these risks are generally considered to be outweighed by the benefits of peripheral blocks.

With respect to the nerve catheters, potential risks to patients with placement are less than with the ultrasound guided block, as these catheters are placed through the skin and into the mastectomy pocket under direct visualization. Additional risks would include the small risk of a post-operative infection related to the catheter. This risk will be minimized by sterile placement, a sterile dressing, and expeditious removal of the catheter within the first post-operative week. As these catheters are standard of care at UC Davis currently, this risk is generally felt to be acceptable.

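### Section 10 ends data collection for randomised patients whose expander is aborted, including pre-operative-arm patients already blocked; this conflicts with Sections 7 and 9 and leaves an exclusion that cannot be checked

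*Combined protocol and SAP*

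**What the plan says.** Patients are randomised after consent on the day of surgery, before the operation, and are told their arm (Section 7). Arm A receives an ultrasound-guided block from anesthesia before surgery. Arm B receives a catheter placed by the operating surgeon once the muscle flap has been raised.

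Section 10 gives one ground for withdrawal without consent: the plastic surgeon judges that the mastectomy flaps will not tolerate an expander, and reconstruction is aborted. It acknowledges that the arms then differ in exposure: "In this circumstance, the pre-op block arm will already have gotten a block", while arm B patients get no catheter. After such a withdrawal, "no other data would be collected regarding their hospital stay, and no survey information collected".

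Two other sections point the other way. Section 9 states: "The EMR of every subject who completes the injection portion of this study will be assessed within 24 hours" of block placement, with no exception for withdrawn patients. Section 7 describes collecting opioid use, nausea and vomiting, pain scores, PACU clearance and discharge times from the hospital stays of all subjects.

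On analysis, Section 8 names a t-test between groups. No section defines an analysis set, a rule for missing data, a replacement rule or an allowance for withdrawals.

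**The concern.** This exclusion is written into the plan and acts after randomisation. The trigger is an intra-operative judgement. The protocol describes no masking, and the operating surgeon places the arm B catheters, so it is a firm inference that the person judging knows the arm. Because outcome collection then stops, nobody could later check whether the excluded patients were balanced between arms or resembled those retained.

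The safety side is more concrete. Aim 1 is to report the safety of the blocks and expects no complications; Aim 2A compares safety between arms. An aborted arm A patient has had the full block exposure. An aborted arm B patient has had none. Any exposed patient lost through this rule therefore comes from arm A, whose technique Section 11 describes as carrying more placement risk than the catheter. A hypothesis of no complications fails on a single event, so losing sight of even a few exposed patients matters.

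**Working it through.** **1. The plan's own figure.** Inputs from Section 8: "we set our alpha = 0.05 and beta (power) = 0.8"; "the mean morphine requirement in the PACU was 2.9 ± 1.861 mg for the Pecs block group"; "our average morphine requirement in the intra-operative placement group would be 2.3 mg"; "we would have to enroll 126 patients in each arm to have an 80% chance of seeing a difference". Sidedness is not stated. With n per arm = 2(z_alpha + z_beta)² SD² / d²:

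- d = 0.6 (2.9 − 2.3), two-sided: 2 × 7.849 × 1.861² / 0.36, giving 152.
- d = 0.58 (unrounded 20% of 2.9), one-sided: 2 × 6.183 × 1.861² / 0.3364, giving 128.

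On these means, 126 is approached only by a one-sided test. That is a separate matter. Below I use the two-sided t-test at 0.6 mg and SD 1.861, where 126 per arm gives 72% power.

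**2. How many patients.** The documents give no abort rate. I assume 3% to 8%: 252 × 0.03 ≈ 8 to 252 × 0.08 ≈ 20 patients. Of these, 126 × 0.03 ≈ 4 to 126 × 0.08 ≈ 10 would be arm A patients already blocked.

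**3. Power if they are excluded and not replaced.** At 5% aborted, 126 × 0.95 ≈ 120 per arm remain, and power is about 70%. At 3% (122 per arm) it is about 71%, and at 8% (116 per arm) about 69%. The loss is small, and there is none if recruitment continues to 252 completers.

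**4. Possible bias from exclusion.** If aborted patients' mean differs from that of retained patients by D, and the aborted shares are q_A and q_B, then

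bias = (q_A − q_B) × D.

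- Equal shares: bias = 0.
- An assumed 4-point imbalance (2% against 6%) with D = 1 mg: 0.04 × 1 = 0.04 mg, and 0.04 / 0.6 = 7% of the target.
- The same imbalance with D = 2.9 mg: 0.04 × 2.9 = 0.116 mg, and 0.116 / 0.6 = 19%.

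The upper case is extreme: against a mean of 2.9 mg, aborted patients would have to use no opioid at all.

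**5. Effect of keeping them, as assigned.** Aborted arm A patients have a block and aborted arm B patients have none, so among them the difference may favour arm A. If that gap is g and the abort rate is r in both arms,

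expected difference = (1 − r) × 0.6 − r × g.

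At an assumed r = 5%, with n = 126 per arm and a two-sided test:

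| Gap g among aborted patients | Expected difference | Power |
|---|---|---|
| 0 mg | 0.57 mg | about 68% |
| 1 mg | 0.57 − 0.05 = 0.52 mg | about 60% |
| 2 mg | 0.57 − 0.10 = 0.47 mg | about 51% |
| 4 mg | 0.57 − 0.20 = 0.37 mg | about 35% |

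The 4 mg row uses the block-against-control difference quoted in Section 8 (6.9 − 2.9). Aborted patients have a smaller operation, so the true gap could be lower; the documents do not say.

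**6. The sections side by side.** For an arm A patient who is blocked and then aborted, Section 9 requires a record check within 24 hours of the block. Section 7 includes the patient's hospital stay among the data collected. Section 10 ends collection once the patient has woken and been told. All three cannot be followed as written. Section 7 also relies on PACU monitoring, and on a chest radiograph if unexplained hypoxia appears, to detect pneumothorax. Much of that period falls after Section 10 has stopped collection.

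**The case against.** The strongest reply is that the rule is the same in both arms and its stated trigger, flap viability, is an anatomical reason handled under standard practice. If aborts do not depend on arm, excluding them gives no expected bias. It also answers a sensible question: what the blocks do in patients who actually have the reconstruction. Keeping everyone is not free either. As the table shows, an as-assigned analysis can be moved by more than the bias it is meant to prevent. All of this stands. It is why I do not insist on which analysis is primary, and why the bias is put as a risk.

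The reply does not answer the conflict with Sections 7 and 9, or the fact that without follow-up nobody can show that aborts were in fact unrelated to arm.

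A reader might also infer four stronger things that the documents do not support:

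- **Recorded data are thrown away.** Section 10 says only that no further data are gathered. It excludes already collected data from analysis for one patient, the former control-arm subject.
- **Blocked patients are definitely removed from the safety count.** Section 9 makes no exception for withdrawn patients, and its record check and serious-event reporting may be meant to continue. The sections are in tension; the outcome is open.
- **The randomised comparison is broken.** That needs arm-dependent aborting, which is hypothetical.
- **Section 6 limits chart outcomes to survey completers.** Its phrase "after surgery and survey completion" describes when the study endpoint is reached. It does not define who is analysed for chart-based outcomes.

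**Conclusion.** The point holds in this form: Section 10 contradicts Sections 7 and 9, exposes the Aim 1 and 2A safety results to a denominator short of exposed patients from one arm only, and creates a post-randomisation exclusion whose size and balance cannot be verified. The textual conflict is certain. The surgeon's knowledge of the arm is a firm inference.

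The numerical consequences rest entirely on assumed abort rates and outcome differences. The efficacy bias may be nil, and is modest in the illustrative case. The power loss from exclusion is one to four percentage points at most over the assumed 3% to 8%. The case for change therefore rests mainly on safety accounting and transparency. It should be settled before the data are analysed.

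**What to change.** No change to the clinical decision to abort is suggested. The changes concern data and analysis:

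1. Reconcile Section 10 with Sections 7 and 9, stating that withdrawal for an aborted expander does not end the safety check or chart collection.
2. Continue chart collection for every randomised patient, and surveys with consent. The consent form should say so.
3. Keep every patient who received a block in the safety denominator.
4. Report the number of aborted expanders, with reasons, by arm.
5. Present results for all patients as assigned and for patients with an expander placed, and name in advance which is primary and why.

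Items 1 to 4 cost protocol wording and chart review for roughly 8 to 20 patients at the assumed rates. Item 5 needs a real decision. If the as-assigned result is primary, power at a 5% abort rate could lie anywhere from about 68% down to about 35%, depending on the gap among aborted patients, against about 70% if they are excluded. If the expander-placed result is primary, the counts by arm and the as-assigned result let readers judge the exclusion.
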